**Impact of Changing Cannulation Strategies on Neurologic Injury in Infants with
Respiratory Failure: HUM00236110**

PI: [name]

Document Date: September 19, 2023

Aims and Approach:

From 2019-2021, there was increased use of venoarterial (VA) extracorporeal membrane oxygenation (ECMO) for infants with respiratory failure, up to 92% of neonatal respiratory support in 2021. Our primary aim is to estimate the average effect on the rate of neurologic injury of VA ECMO versus venovenous (VV) among infants with respiratory failure over the period 2013-2018, during which clinicians could choose either cannulation strategy. We will estimate this causal effect using an inverse propensity weighted (IPW) approach. Secondly, we will project this estimated treatment effect forward into the period 2019-2021. The beginning of this period roughly corresponds to start of increased use of VA ECMO. Under the assumption of a homogenous treatment effect across both study periods, we will estimate the rate of neurologic injury that *would have* occurred in 2019-2021, had the rate of VA ECMO *not* increased relative to pre-2019 levels. We hypothesize that our results will point to an increased rate of neurologic injury starting in 2019 due to the increased use of VA ECMO.

Outcome:

The outcome will be the composite occurrence of neurologic injury (ischemic stroke, intracranial hemorrhage, and brain death) that arises during critical illness supported by ECLS as reported to the Extracorporeal Life Support Organization (ELSO) registry, coded as a 0/1 variable (0 = no occurrence was reported during or after ECMO; 1 = one or more occurrence was reported).

Exposure:

The exposure / treatment of interest is the initial cannulation mode used, coded as a 0/1 variable (0= VV dual-lumen or two-site; 1= VA peripheral cannulation only).

Study Population:

We will analyze data from the ELSO registry. All runs satisfying the following inclusion and exclusion criteria will be included in our study population:

Inclusion criteria:

- Patient weighed less than or equal to 10kg at start of ECMO
- Pulmonary support was the indication for ECLS
- Initial cannulation strategy was VV or VA
- The run occurred during the period 2013-2023

Exclusion criteria:

- Patient had CDH
- Patient was post-cardiotomy
- Non-conventional initial cannulation strategies were employed, such as
 - Central Cannulation (surrogate for inability to achieve peripheral cannulation)
 - Veno-veno-arterial ECMO
 - Initial cannulation approach reported as “other”
- Patient was transported into or out of ELSO center on ECMO support
- Patient had pre-ECLS Cardiac Arrest
- Patient did not have subsequent ECMO runs in the ELSO registry

In addition, to the above criteria, all otherwise-eligible runs from centers that do not have at least one eligible run from each exposure group during the study period will be excluded.

Statistical Analysis Plan:

Step 1 will estimate the probability of being in the exposure group during a period when clinicians could choose either VV or VA ECMO. Among the subsample of patients from the period 2013 to 2018, we will fit a logistic regression model using pre-cannulation center and patient factors to predict the probability of a patient receiving VA ECMO.

We will include in this model factors that precede the start of ECMO and are posited to be associated with both the choice of cannulation strategy as well as the risk of neurologic injury.

We will include the following predictors in the propensity score model:

Unit Type- multinomial categorical

Admitted at birth -binary

Age at cannulation (days)- continuous

Gestational age (semi-continuous to 38 weeks, term infants will older infants will be classified together)

Transfer into the ECMO center- binary

Weight (cont)

Sex- binary

Intubation to Time On (continuous)

Pre-ECLS pH (continuous)

Pre-ECLS pCO₂ (continuous)

Pre-ECLS PO₂ (continuous)

Pre-ECLS HCO₃ (continuous)

Pre-ECLS FiO₂ (continuous)

Pre-ECLS Mean Airway Pressure- oscillator (continuous)

Pre-ECLS Mean Airway Pressure- conventional (continuous)

Pre-ECLS Mean Arterial Pressure (continuous)

Pre-ECLS Pulse Pressure (continuous)

Pre-ECLS Renal Replacement Therapy- binary

iNO- binary

Inhaled epoprostenol- binary

Therapeutic Hypothermia- binary

Vasoactive Infusions- binary

Diagnoses

Meconium Aspiration Syndrome- binary

HIE- binary

Pulmonary hypoplasia- binary

Respiratory Distress Syndrome- binary

Persistent Pulmonary Hypertension- binary

Pulmonary Hypertension- binary

Sepsis- binary

Asthma- binary

Bronchiolitis- binary

Pneumonia - binary

Pertussis- binary

PDA- binary

We will also take into account each center's typical proclivity for VV versus VA ECMO, using either a mixed-effects modeling strategy or the surrogate indicator approach of Li, Zaslavsky, and Landrum (2007)

In **Step 2**, we will estimate the average treatment effect (ATE) of VA-ECMO in the period 2013-2018 using an IPW approach. We will estimate the ATE using an appropriate estimator that takes into account the clustered nature of the data (runs clustered within ELSO center).

Because the availability of VV ECMO cannulas appropriate for infants changed in 2019, we expect that at this point and afterward clinicians generally chose VA ECMO support more often than they otherwise would have. Using the propensity score model developed in Step 1, we will calculate propensity scores for patients cannulated during 2019-2021, estimating the propensity that a given patient would have received VA ECMO had they received ECLS support in 2013-2018. Using these estimated propensities, in **Step 3**, we will project this estimated ATE from the 2013-2018 cohort into the 2019-2021 cohort, thereby estimating what the rate of neurologic injuries would have been had the availability of VV ECMO cannulas not changed (and assuming a homogenous treatment effect of VA ECMO across periods). If there is a large enough sample size, we will perform a sensitivity analysis in a cohort from 2022-2023, during which there was increased availability of VV-ECMO cannulas and increasing use of VV-ECMO support.

Missingness in the predictors

We anticipate that there will be sporadic missingness in the predictors used to construct the propensity scores. We will use the approach recommended in Leyrat, et al. (2019) to incorporate the partial information available from observations with missingness. Specifically, we will create multiply imputed versions of the data, estimate a separate ATE for each of these completed datasets, and then combine the estimated ATEs across imputations to obtain a single estimated ATE.

References

Leyrat, C., et al. (2019). "Propensity score analysis with partially observed covariates: How should multiple imputation be used?" Stat Methods Med Res **28**(1): 3-19.
Li, F., et al. (2007). Propensity score analysis with hierarchical data. Proceedings of the American Statistical Association Joint Statistical Meetings.

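### Overlap between VA and VV is secured only by center; without a patient-level support rule, the whole-cohort ATE may not be identified for some infants, such as the smallest

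*SAP*

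**What the plan says.** The Study Population section limits size on one side only: "Patient weighed less than or equal to 10kg at start of ECMO". Neither criteria list has a lower limit on weight or gestational age, or a requirement that VV was possible for the infant. Exposure is coded "0= VV dual-lumen or two-site; 1= VA peripheral cannulation only". One exclusion does concern feasibility, "Central Cannulation (surrogate for inability to achieve peripheral cannulation"), but it deals with failed peripheral access and has no counterpart for VV.

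The only overlap rule is at center level: runs from "centers that do not have at least one eligible run from each exposure group during the study period will be excluded". The inclusion window is 2013-2023, so on a literal reading a center's single VV run could even fall outside 2013-2018.

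The propensity model in Step 1 includes weight as a continuous predictor and "Gestational age (semi-continuous to 38 weeks"). For the primary analysis, Step 2 states that "we will estimate the average treatment effect (ATE) of VA-ECMO in the period 2013-2018 using an IPW approach". It asks for an estimator that allows for clustering by center. It names no trimming, truncation, overlap weights or check of common support.

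**The concern.** Inverse propensity weighting identifies the ATE only if every type of infant in the cohort had some chance of either mode. A center with one VV run and many VA runs passes the SAP's rule, yet this says nothing about whether any VV run was in an infant of a given size.

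Suppose a group of infants received only VA. They enter the weighted VA mean, and no similar infant represents them in the weighted VV mean. If their injury risk is higher for reasons unrelated to cannulation, the VA mean rises and the contrast shows harm that VA did not cause. That is the direction of the SAP's stated hypothesis, and Step 3 would carry the error into 2019-2021.

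**Working it through.** The SAP gives no event rate, sample size or VA share by weight, so there is no figure of its own to reproduce. All rates and shares below are assumptions. The true VA effect is zero throughout, weights are normalised, and the logit of the propensity is taken as linear in weight. The SAP says only that weight is continuous, so linearity is also an assumption.

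**1. Closed form.** Let a share s of infants always receive VA with injury risk r_s, and let the rest have risk r_o. With correct scores, false excess = s × (r_s − r_o). At s = 5%, r_s = 35% and r_o = 15%: 0.05 × 20 = 1.0 point.

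**2. Simulation with a jump in risk.** Weight is lognormal with median 3.6 kg, VV is never used in the lightest share, and r_o = 15%. There were two sets of runs, with 200,000 and 400,000 infants per case.

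| Share | r_s | s × gap (points) | Simulated false excess (points) |
|---|---|---|---|
| 3% | 25% | 0.3 | 0.3-0.4 |
| 5% | 25% | 0.5 | 0.7-0.8 |
| 10% | 25% | 1.0 | 1.3-1.6 |
| 3% | 35% | 0.6 | 0.8-0.9 |
| 5% | 35% | 1.0 | 1.4 |
| 10% | 35% | 2.0 | 2.8-2.9 |

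A further set with the same null effect, linear logit and normalised weights gave 0.2-2.5 points, so the range over all sets is 0.2-2.9.

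The simulated values exceed the closed form because the linear model gives the always-VA infants mean scores of only 0.71-0.75, although their true score is 1. Each then gets a weight of about 1/0.75 = 1.33 to 1/0.71 = 1.41. At 10% and 35% this gives 2.0 × 1.33 = 2.7 to 2.0 × 1.41 = 2.8, close to the simulated value.

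**3. Smooth risk.** With no jump and shares of 3-10%, the false excess was 0.1-0.6 points when risk rose smoothly to 19-24% at the 5th weight percentile. It was 0.7-1.3 points when risk reached about 30% there.

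**4. Do routine safeguards catch it?** A second setup used weight with median 3.3 kg, log-SD 0.35, and 400,000 infants per draw. Injury log-odds fall by 0.2 per kg, with an optional extra step below the assumed cut-off. False excess in points:

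| Always-VA share (cut-off) | Extra log-odds | Whole cohort | Scores trimmed to 0.1-0.9 | Overlap weights | Restricted to VV-used weights |
|---|---|---|---|---|---|
| 7.6% (2.0 kg) | 0 | −0.02 | 0.31 | −0.08 | 0.04 |
| | 0.5 | 0.74 | 0.93 | 0.51 | −0.03 |
| | 1.0 | 2.17 | 1.96 | 1.65 | −0.09 |
| 15% (2.3 kg) | 0 | 0.27 | −0.03 | 0.17 | −0.03 |
| | 0.5 | 1.74 | 1.86 | 1.23 | −0.14 |
| | 1.0 | 3.78 | 3.86 | 2.73 | −0.17 |

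The 15% share lies outside the 3-10% range and is shown as a stress case. The trimmed and restricted columns are separate draws. With about 60% VA, the simulation standard error is near √(0.15 × 0.85/240,000 + 0.15 × 0.85/160,000) = 0.12 points, so the restricted column is compatible with zero.

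The highest fitted score was 0.81 at the 2.0 kg cut-off and 0.86 at 2.3 kg. Trimming at 0.9 therefore removes none of the always-VA infants. Overlap weights built on the same scores reduce the bias but do not remove it.

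**5. Step 3.** On its plain reading, the projected excess is the ATE times the rise in VA use, so a biased ATE passes through in proportion. In addition, always-VA infants with fitted scores of 0.71-0.8 would be counted as if 20-29% of them would have had VV in 2013-2018.

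**The case against.** The strongest reply is that nothing in the SAP shows that an always-VA group existed in 2013-2018. VV includes two-site cannulation, so a misfit of one cannula type need not rule VV out. Weight and gestational age are both in the propensity model. Where risk changes gently with size, the bias can be indistinguishable from zero (−0.02 points in the first row of the second table). The higher risk of the smallest infants is also not stated; the SAP says only that its predictors are thought to relate to both choice and injury. All of this stands, and it is why the size is given as a range that starts at nil.

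It does not dispose of the point. Adjustment cannot supply VV infants where there are none, and leaving the estimator open in Step 2 does not commit the analysts to look.

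A reader might infer two stronger claims, and the text supports neither:

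- **That the estimand covers only infants who could have had either mode, so that the criteria contradict it.** The clause "during which clinicians could choose either cannulation strategy" describes the calendar period, not each patient. The gap is an omission, not a contradiction.
- **That the SAP itself treats cannula fit as deciding the mode.** Its remark on VV cannulas concerns a change in availability in 2019. It does not say that some infants were too small for VV before then.

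**Conclusion.** The point holds as a conditional weakness. The SAP targets a whole-cohort ATE while securing overlap only by center, and nothing planned would detect infants with no VV counterpart.

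With an assumed 3-10% always-VA share and an assumed higher risk in those infants, the false VA excess is about 0.1-1.3 points under smooth risk and 0.2-2.9 points under a jump. The top value needs both a 10% share and a 20-point jump. The bias is nil if VV was used at all weights, and with normalised weights it is upward only if the always-VA infants carry the higher risk. The documents do not support saying that the planned analysis will produce a false VA harm, only that it could and that the plan would not reveal it.

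**What to change.** Before any outcome analysis:

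- Tabulate 2013-2018 exposure by weight band, without outcome data. Tabulate by gestational age among neonates only. The cohort runs to 10 kg and includes diagnoses such as bronchiolitis and pertussis, so maturity at birth is a poor guide to current size in older infants.
- Restrict the primary analysis and the Step 3 projection to the contiguous weight range in which VV was actually used. Set a minimum number of VV runs per band in advance, so that a stray run in a sparse tail does not set the floor. A percentage alone is fragile: with an assumed 3,000 runs, a true cut-off of 2.5 kg and 2% stray VV use below it, taking the lowest band with at least 5% VV put the floor too low in 22% of 2,000 simulations.
- Report how many runs are excluded, and name the estimand as the effect in infants within the common-support range.
- Show the unrestricted cohort as a sensitivity analysis.

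The cost is one exposure table and a few sentences in the SAP. The cohort may be slightly smaller, and the result will say nothing about infants outside the range. If the table shows VV at every weight, nothing is lost and the overlap assumption is documented.

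### The last exclusion criterion is inverted: as written it removes every infant without a later ECMO run and keeps only those with one

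*SAP*

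**What the plan says.** The SAP's Study Population section makes the two lists of criteria operative: "All runs satisfying the following inclusion and exclusion criteria will be included in our study population". The last bullet under Exclusion criteria is "Patient did not have subsequent ECMO runs in the ELSO registry"; the bullet just before it is "Patient had pre-ECLS Cardiac Arrest".

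A separate sentence then drops "all otherwise-eligible runs from centers that do not have at least one eligible run from each exposure group", so the centre filter depends on which runs have already been judged eligible.

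The primary aim, under Aims and Approach, is the "average effect on the rate of neurologic injury of VA ECMO versus venovenous (VV) among infants with respiratory failure". It has no restriction to infants with repeat runs. Step 2 of the analysis names one level of clustering: "runs clustered within ELSO center".

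**The concern.** An exclusion list works in one direction: if the stated condition is true, the patient or run leaves. Applied to the last bullet, that removes infants whose first run was their only one and keeps those who went on to another. This is the reverse of any cohort the aim could describe.

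The rule fixes who enters the propensity model, the ATE for 2013-2018 and the projection to 2019-2021. It also feeds the centre filter, so a wrong rule could remove whole centres. The literal rule would further distort the outcome: brain death is part of the composite, and an infant with brain death on an only run has no later run, so that component would nearly vanish.

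Seeing the inversion does not tell an analyst what to do instead. At least two repairs fit, and they give different cohorts.

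**Working it through.** **The text.** The other exclusion bullets are CDH, post-cardiotomy status, non-conventional cannulation, transport on ECMO and pre-ECLS cardiac arrest. In each, presence of the feature removes the patient or run. The last bullet names an absence, so what it removes is the set with zero later runs.

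Could the word *satisfying* in the lead sentence make each bullet a condition for entry? No: CDH and pre-ECLS arrest would then also be required for entry.

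**Candidate repairs.**
- (A) Analyse each infant's first run and drop later runs.
- (B) Exclude patients who had a later run. This is closest to the wording. Applied per patient it drops all of a repeat-run infant's runs; applied per run it keeps that infant's last run.

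Clustering by centre alone fits one run per infant but does not decide between A and B.

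**Size.** The SAP has no figure to reproduce. If a share r of otherwise eligible infants has a later run, the literal rule removes 1 − r. Assuming r = 1% to 10%, that is 99% to 90%.

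Everything below is also assumed, and the SAP supports neither direction between modes:
- first-run injury risk p = 0.15 (VA) and 0.12 (VV), a true difference of 3.0 points;
- later-run rate r in each arm;
- injury multiplies the chance of a later run by k = 0.5, 1 or 2, the same in both arms.

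The chance of a later run is then q0 = r/(1 − p + kp) without injury and q1 = k·q0 with injury.

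*Literal rule*, first-run injury among infants with a later run: kp/(1 − p + kp). The rate r cancels.
- k = 2: 0.30/1.15 − 0.24/1.12 = 26.09% − 21.43% = 4.66 points.
- k = 0.5: 0.075/0.925 − 0.06/0.94 = 8.11% − 6.38% = 1.73 points.

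*Repair B, per patient*: p(1 − q1)/[p(1 − q1) + (1 − p)(1 − q0)]. For rates of 3% (VA) and 8% (VV) with k = 2:
- VA: q0 = 0.03/1.15 = 0.0261, q1 = 0.0522, risk 0.1422/0.97 = 14.66%.
- VV: q0 = 0.08/1.12 = 0.0714, q1 = 0.1429, risk 0.1029/0.92 = 11.18%.
- Difference: 3.48 points.

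*Repair A, first-run injuries only*: 3.0 points throughout.

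*Repair A, later-run injuries also counted*: p + (1 − p)·q0·h, with injury risk in the later run h = 0.10 to 0.20. For 3%/8%, k = 1, h = 0.10: 15.255% − 12.704% = 2.55 points.

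| Later-run rate VA / VV | B, k = 0.5 | B, k = 2 | A with later-run injuries, range over k and h |
|---|---|---|---|
| 1% / 3% | 2.90 | 3.18 | 2.62 to 2.84 |
| 3% / 1% | 3.16 | 2.75 | 3.14 to 3.36 |
| 5% / 5% | 3.07 | 2.91 | 2.95 to 2.99 |
| 3% / 8% | 2.72 | 3.48 | 2.05 to 2.59 |
| 8% / 3% | 3.43 | 2.33 | 3.36 to 3.91 |

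With k = 1, the literal rule and B both give 3.00 in every row. The last column is a change of estimand, not a bias.

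**The case against.** The strongest reply is that this is a slip nobody would implement: with any modest later-run rate the literal rule empties most of the cohort and would be noticed at once. That is fair on likelihood. The case for correction therefore rests on an operative rule being wrong as written, not on a forecast that the wrong analysis will be run. Noticing the slip also leaves the choice among A, B per patient and B per run to whoever extracts the data.

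A second reply is that the figures rest on invented inputs and, because k is the same in both arms, are not bounds. That stands. They show only that the literal rule can do more harm than B under the same inputs, and that A and B differ modestly.

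A third is that recommending A goes beyond repairing a typo, since B is closer to the text. This also stands in part. The argument for A is conditional. B makes eligibility depend on an event after cannulation, which a propensity model of "factors that precede the start of ECMO" cannot correct, but harm follows only if later runs relate to injury; with k = 1 there is none. A is thus a recommendation subject to the sponsor's confirmation.

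**Conclusion.** The concern holds. The criterion defines the opposite of a usable cohort, contradicts the aim and is corrected nowhere in the SAP. Confidence is high for the inversion, and that conclusion needs no assumed figure. It does not extend to which repair was intended.

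Correcting the polarity and stating the rule is essential. The choice between A and B is a lesser point. Under the assumptions shown, B moves a 3.0-point difference to between 2.3 and 3.5; the direction depends on which mode has more later runs and on whether injury makes a later run more or less likely. The true size is unknown.

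**What to change.** 1. The sponsor confirms the intended rule, and the SAP states it with its unit, patient or run.

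2. Recommended, subject to that confirmation: *Only the patient's first ECMO run in the registry is eligible. Later runs are not analysed as separate observations, and patients are kept whether or not a later run occurred.* The sponsor should check that first run in the registry is meant, rather than first eligible run. The two differ for an infant whose first run was ineligible but whose later run was not.

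3. Under this rule, also state whether an injury reported in a later run counts toward the first run's outcome. The Outcome section codes zero as "no occurrence was reported during or after ECMO", which leaves this open.

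4. If the sponsor confirms B, reverse the line and name the unit, for example: *A patient with any later run is excluded, with all of that patient's runs.* The SAP should then say that eligibility depends on an event after cannulation. Attribution of later-run injuries does not arise per patient. If B is applied per run, the retained last run follows earlier ones, and the SAP must say which run an injury belongs to.

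The cost is a few sentences in the SAP and one filter in the data extraction, with no new data.

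### The propensity model uses oscillator and conventional mean airway pressure as two continuous terms, with no ventilator-mode term and no rule for a pressure that does not apply

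*SAP*

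**What the plan says.** In the Statistical Analysis Plan section, Step 1 fits a logistic model for VA use in 2013-2018. The predictor list opens with "We will include the following predictors in the propensity score model". It has 34 named items, and the SAP adds a centre term. Two items are "Pre-ECLS Mean Airway Pressure- oscillator (continuous" and "Pre-ECLS Mean Airway Pressure- conventional (continuous". None is ventilator mode or type. The stated ground for inclusion is that the factors are "posited to be associated with both the choice of cannulation strategy as well as the risk of neurologic injury".

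The section Missingness in the predictors says: "We anticipate that there will be sporadic missingness in the predictors used to construct the propensity scores". The chosen method is meant "to incorporate the partial information available from observations with missingness", and its content is that "we will create multiply imputed versions of the data, estimate a separate ATE for each of these completed datasets", followed by pooling. The SAP has no not-applicable category, no combined pressure variable, no indicator and no complete-case rule.

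Step 3 reuses the model: "Using the propensity score model developed in Step 1, we will calculate propensity scores for patients cannulated during 2019-2021".

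**The concern.** A conventional-ventilator pressure for an infant who was only on an oscillator is not a lost measurement; it does not exist. A logistic model with both pressures as main terms still needs a number in each column for every infant, and imputation is the only route the SAP gives. An analyst who follows it literally will invent the second pressure.

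That step removes information. Whether an infant was oscillated shows in the raw data through which field is filled. Once both fields are filled for everyone, it no longer does. If mode is related to VA choice and to neurologic injury beyond the listed covariates, that confounding stays in the weighted ATE and passes into the projected 2019-2021 injury rate. The SAP posits confounding only for the factors it lists, so this further link is an assumption. Splitting pressure by ventilator does suggest that the authors regard the device as relevant.

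**Working it through.** **No planned figure applies.** The SAP gives no number on this point to reproduce. The check is a short argument followed by simulation. Every numerical input below is assumed.

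**Argument.** Let V be mode (1 = oscillator). Among infants with one pressure, oscillator pressure is observed only when V = 1. The imputation model is fitted to the observed values and fills in the V = 0 infants from the same conditional distribution given the other covariates, exposure and outcome. The completed column then has the same conditional distribution in both modes, and likewise for conventional pressure. The two columns no longer separate V = 1 from V = 0.

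**Main simulation: inputs**
- n = 20,000; 10 replicates; 3 imputations; 6 cycles of chained normal regressions; Hajek-type IPW; true risk difference (RD) 0.
- S and X ~ N(0,1) stand for the other covariates and are in every propensity model; e is standard normal noise.
- logit P(V = 1) = 0.3 + 0.5S + dX, with d = 0, 1, 2. S and X then predict mode with AUC 0.63, 0.76, 0.87, and about 55-57% are oscillated.
- z = 0.4S + 0.917e. Pressure in use = 18 + 3z (oscillator) or 13 + 3z (conventional). Where both are recorded, the other pressure uses 0.7z + 0.714e in place of z.
- Exposure logit = 0.5 + gA(V - mean) + bz + 0.4S. Outcome logit = -1.4 + gY(V - mean) + bz + 0.4S.
- (gA, gY) = (0, 0), (0.5, 0.4), (0.8, 0.6), (1.2, 0.8); b = 0, 0.2, 0.5; share with both pressures 0, 10%, 30%.
- Scenarios: 4 x 3 x 3 x 3 = 108, of which 3 x 3 x 3 x 3 = 81 have a mode effect.

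Bias = RD minus the RD from the same data weighted on true mode and pressure. Imbalance left = weighted VA-VV difference in the proportion oscillated, divided by the unweighted difference.

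**Not-applicable pressure imputed, mode effect present, 10-30% with both, outcome in the imputation model**

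| AUC for mode | Imbalance left | RD bias (points) |
|---|---|---|
| 0.63 | 66-88% | +0.13 to +3.44 |
| 0.76 | 59-77% | -0.09 to +2.96 |
| 0.87 | 50-62% | -0.09 to +2.34 |

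Bias was -0.1 to +0.9 under the weakest mode effects and +1.6 to +3.4 under the strongest. The largest standard error with the outcome in the imputation model was 0.13 points; the two values of -0.09 have standard errors of 0.04-0.05.

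**Variations**
- Outcome left out of the imputation, 10-30% with both: +0.67 to +3.43, +0.58 to +3.04 and +0.43 to +2.48 points for the three AUCs.
- No infant with both, outcome in: -2.47 to +3.34, -2.63 to +2.82 and -2.64 to +2.37. Outcome out: +0.39 to +3.43 overall.
- No mode effect but b = 0.5, outcome in: about -3.2 to -2.9, -0.6 and -0.2 points at 0, 10% and 30% with both. This is a second mechanism: imputing pressures that are rarely or never seen together.
- No mode or pressure effect: 0.0.

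**Alternative coding**
- Mode in use plus nested pressure: -0.06 to +0.04 points in all 81 mode-effect scenarios, with 0-1% of the imbalance left.
- Not-applicable pressures set to zero, no mode term: -0.19 to +0.10 when no infant has both, but +0.05 to +3.72 at 10-30% with both (9-31% of imbalance left). This is not a substitute.

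**Smaller simulation, different inputs.** n = 3,000, 40 replicates, 5 imputations, one pressure per infant, 50% or 70% oscillated, mode log-odds 0.8 on VA and 0.6 on injury. The standardised difference in mode after imputation and weighting was 0.35-0.40 (crude 0.34-0.39), 0.33-0.35 (crude 0.52-0.56) and 0.22-0.23 (crude 0.62-0.65) as the other covariates predicted mode not at all, moderately and strongly. Each agreed within 0.004 with weighting on the other covariates alone, so the imputed pressures added essentially no balance on mode. The spurious RD was about 0 to 2 points. With mode plus nested pressure the standardised difference was 0.00 and the RD was within about 0.4 points of zero.

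**The case against.** The SAP never says a not-applicable pressure will be imputed. A blank left because the ventilator was not used is systematic, so a rule for sporadic gaps arguably does not cover it, and the coding might be settled in a document not at hand. Harm needs three things the SAP does not state: many infants with one pressure only, analysts who impute the other, and a mode effect beyond 34 predictors and centre. The simulations have only one or two background covariates and no centre clustering. The sign of the bias is not fixed, and some of it comes from the second mechanism rather than from loss of mode. The near-zero bias under the alternative coding is partly built in, because true mode is known there and the model matches how the data were generated.

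Most of this stands, and it limits any claim about size. It does not remove the gap. If the imputation rule excludes these blanks, the listed model cannot be fitted to infants with one pressure, because no other rule is given. If it includes them, mode drops out of the completed data. The SAP has a section on missing predictors, and this choice can change the primary estimate, so it belongs there. Other specifications could also work; what matters is that one is stated and keeps mode in the model.

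**Conclusion.** The concern holds. As written, the SAP either leaves its propensity model without values for infants with one pressure or fills them in a way that discards ventilator mode. Whether the ATE is materially biased, in which direction and by how much cannot be determined from the SAP. The simulated biases are illustrations under assumed effects. The problem shrinks if most infants have both pressures recorded, and mode confounding is absent if mode adds nothing beyond the listed covariates. The SAP should be changed on this point; confidence is medium because the shares and effects are unknown.

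**What to change.** Amend the predictor list and the missingness section to state that:
- a pressure for a ventilator not in use is not imputed;
- the model includes a ventilator-mode indicator with pressure nested within mode;
- a pressure is imputed only when it is unrecorded for the mode in use, and mode is imputed too when neither field is filled;
- infants with both pressures are coded by the mode in use where the registry shows it, and otherwise as a separate category;
- the 2019-2021 cohort is coded the same way in Step 3, and weighted balance on mode is reported.

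The cost is SAP wording and some recoding. The remedy is not perfect. With 15% of infants having neither field (assumed), imputing mode and pressure kept bias within 0.03 points but left 7-12% of the imbalance (12 scenarios, 8 replicates, 5 imputations). If mode can only be inferred from which field is filled, infants with both stay ambiguous: at 10% such infants, 6-9% of the imbalance and +0.1 to +0.4 points of bias remained; at 30%, 19-27% and +0.2 to +1.1 points. The SAP does not say whether the registry records mode, so the team should establish this, and count infants with one, both or neither pressure, before fixing the wording.
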